Obtaining human tissue for basic research or biospecimen bank

Survey instrument

None of the above

The following documents are currently attached to this item:

There are no documents attached for this item.

Department budget code

None

Multi-Site Research

Other Sites

No other sites

Management of Information for Multi-Center Research

n/a

The following documents are currently attached to this item:

There are no documents attached for this item.

Protocol

Abstract

Of the many factors contributing to the obesity epidemic, the timing of food consumption is now recognized as a significant contributor to body weight regulation. Disruption of the normal timing of feeding in mice has been found to promote weight gain, alter serum leptin levels, and induce hypothalamic leptin resistance. Delays in daytime eating have also been found to increase the risk of obesity and metabolic syndrome in humans. Disrupting normally-timed sleep-wake cycles produces major effects on body weight, adiposity, and metabolism, but it remains unclear whether meal timing independently plays a causal role in metabolic dysregulation when sleep-wake cycles are unaltered. The purpose of this study is to determine if, controlling for eating and sleep timing, caloric intake, and exercise, daytime vs. delayed eating affects body mass, adiposity, and energy metabolism in healthy adults.

Objectives

Overall objectives

To determine if timing of food consumption (daytime vs. delayed eating) affects body mass, adiposity, and energy metabolism by enrolling 30 healthy men and women in a randomized cross-over design study.

Primary outcome variable(s)

To determine if timing of food consumption (daytime vs. delayed eating) affects body mass (kg) after a period of two months.

Secondary outcome variable(s)

Our secondary outcomes will be assessed before and after each eating condition for a total of four assessment periods. Blood samples will be taken every four hours for 24 hours in the CTSC during each assessment. Metabolic testing and DEXA will occur once at each of the four assessment periods. Specific secondary outcomes include: Amplitude and phase of circadian rhythms of leptin, cortisol, and melatonin; Fasting levels of glucose, insulin, adiponectin, cholesterol, triglycerides, and non-esterified fatty acids; Energy expenditure and fuel oxidation as measured by indirect calorimetry; and Body composition measured using DEXA

Background

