Between UPenn, Penn Medicine, and the population of West Philadelphia, an adequate pool of adults live/work within 5 miles of the Hospital of UPenn. PI [name] recently completed a survey of 201 patients at an obstetrics clinic at Penn Medicine and found 91% had texting access and 79% had a smartphone. Thus, we do not anticipate any problem recruiting 30 healthy adult participants within our inclusion criteria.

Key inclusion criteria

Adults of all races and ethnicities; Age 21-50; BMI 19-30 kg/m²; stable weight (+/- 10 lbs) over the previous 6 months; Women must be pre-menopausal with regular menstrual cycles.

Key exclusion criteria

Regular exercise more than 4 d/wk, for 60 min measured by exercise logs and actigraphy; normal activity levels are required throughout the study (+/-30 min/wk of baseline level). Unstable, serious medical conditions; use of medicine linked to weight gain/loss; cancer, diabetes, or autoimmune disease; use of illicit drugs, melatonin, diuretics or hypnotics; current weight loss program; presence of a sleep disorder (determined by surveys and actigraphy); night shift work; extreme chronotypes (extreme larks or night owls); habitual waking outside of 0600 h-0900h; habitual bedtime outside of 2200h to 2400H; and sleep duration outside of 6.5 to 8.5 h/night. Psychiatric exclusions will be depression (Patient Health Questionnaire-9 score 9), lifetime bipolar disorder, psychosis, or lifetime eating disorder; or any other severe psychiatric disorder judged to interfere with study adherence as assessed by the MINI International Neuropsychiatric Interview version 6.0.0. Participants must be non-smokers. Participants will be excluded if they are pregnant. A urine pregnancy test will be conducted during the study screening visit. A urine drug test will also be collected at the screening visit.

Vulnerable Populations

Children Form

Pregnant women (if the study procedures may affect the condition of the pregnant woman or fetus) Form

Fetuses and/or Neonates Form

Prisoners Form

Other

None of the above populations are included in the research study

The following documents are currently attached to this item:

There are no documents attached for this item.

Populations vulnerable to undue influence or coercion

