After an initial phone screen to determine eligibility and assess availability, the screening visit will be scheduled. Study staff will complete a clinical interview assessing typical eating and sleep patterns, weight history, and psychiatric status. Participants will undergo a medical history and physical, and their weight, height, and waist circumference will be measured. Participants will receive logs to record food, physical activity (detailing deliberate bouts of exercise), and sleep-wake, as used in our previous studies of NES, and an actigraph to wear for 10d. Upon completion they will return the completed logs and actigraphs. If they meet the inclusion criteria after this 10d screening period, they will be scheduled to undergo a history and physical at the CTRC and, subsequently, their baseline assessment and randomization. After the 28-h baseline assessment, participants will be randomized to begin the study with either the daytime or delayed eating condition, and they will receive their first 3d of food. The participants will also receive food, sleep, and exercise logs and actigraphs, which they will use for the study duration. Assessments will be conducted at four points: 1) baseline; 2) after completion of condition 1; 3) after the 2 wk wash-out period; and 4) after completion of condition 2. Each assessment will include 28h at the Clinical and Translational Research Center (CTRC) where participants will eat according to their typical schedule (for points 1 and 3) or their assigned schedule - daytime or delayed (for points 2 and 4). 10mL (2 teaspoonfuls) of blood will be drawn at 4h intervals (0800h, 1200h, 1600h, 2000h, 2400h, and 0400h) to measure amplitude and phase of circadian rhythms of leptin, cortisol, and melatonin. Fasting levels of glucose, insulin, adiponectin, cholesterol, triglycerides, and non-esterified fatty acids (NEFAs) will be measured at the beginning of each assessment session. All blood assays will be performed by [name]. and her staff at the RIA Core Lab of the Penn Diabetes Center. Energy expenditure measurement: On the morning after blood draws and an overnight fast, indirect calorimetry will be used to assess energy expenditure and fuel oxidation (respiratory quotient). One technique for assessing energy expenditure involves measuring a proxy of heat loss using indirect calorimetry. The body's energy production is dependent on oxygen (O₂) and each liter of O₂ consumed by the body is equivalent to ~5 kcal; therefore, O₂ consumption (VO₂) provides an accurate indirect way of measuring a person's energy expenditure (Leonard, 2012). In addition to VO₂, the respiratory quotient (the ratio of CO₂ production (VCO₂) to VO₂), can be measured. Because the caloric equivalent for each liter of O₂ consumed varies as a function of respiratory quotient, both measurements are required to calculate resting metabolic rate. Diet induced thermogenesis represents the increase in energy expenditure above resting metabolic rate divided by the energy content of the food ingested and is commonly expressed as a percentage. In this study, a Parvo Medics True One 2400 Metabolic Monitor will be used to measure indirect calorimetry. The metabolic monitor is a compact, integrated metabolic measurement system which contains O₂ and CO₂ analyzers, a device for measuring breathing (ventilation) rates, a gas sampling system, and a computer interface that allows for the transfer of raw data. A canopy/hood interface is used to collect air samples. This metabolic monitor has been widely used in clinical and experimental settings and has been validated (Bassett et al., 2001; Cooper et al., 2009). The metabolic monitor will assess indirect calorimetry for each subject a total of 4 times (once during each inpatient assessment). During each of the four assessments, subjects resting metabolic rate will be assessed the morning after continuous blood draws with each measurement lasting 45 minutes (10-15 minute adaptation period, followed by 30 minutes of testing). During the

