The risk to participants in this trial have been carefully considered and minimized to the extent possible. Every effort has been made to provide a study in which the safety of the research participants is protected. During this study participants will be asked personal questions such as their weight, age, eating habits, and mood. During the outpatient phase participants will experience the inconvenience of wearing actigraphs and keeping journals of their food intake, sleep, mood, and physical activity, all of which pose minimal risk. The interviews and paper-and-pencil assessments present little risk to participants beyond those experienced in daily life. Blood draws. During the inpatient assessments, participants will experience the discomfort of the initial venapuncture and blood withdrawal system and the possibility of small bruises at the site of the needle, dizziness, or fainting shortly after having blood drawn. Local clots may form, and infections may occur, but these are rare. DEXA. This research study involves exposure to radiation from the DEXA scans and therefore participants will receive a radiation dose. The radiation exposure from a whole body DEXA scan is 0.04 mrem which is equivalent to the exposure from a lateral chest X-ray. At doses much higher than participants will receive, radiation is known to increase the risk of developing cancer after many years. At the doses participants will receive, it is very likely that they will see no effects at all. Metabolic Testing. The study involves restraining participants from eating for a period of at least 10 hours (overnight), which may be uncomfortable. If unforeseen risks are seen, they will be reported to the Office of Research Integrity and Compliance. If any events occur that might be related to the study, the participant will be instructed to bring them to the attention of their personal physician, as well as study staff.

Potential Study Benefits

There may be no direct benefit to subjects as a result of participation in the study. Participants may increase their knowledge of their eating and sleeping behaviors. Participation will contribute important data for the field of weight management, which may benefit persons more broadly.

Alternatives to Participation (optional)

The only alternative to participation is to choose not to participate in this study.

Data and Safety Monitoring

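### Pregnancy is tested once, at screening, and not re-verified at the four later DEXA and outcome assessments; the visible text does not say how an on-study pregnancy is handled

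*Combined protocol and SAP*

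**What the plan says.** Key exclusion criteria: "Participants will be excluded if they are pregnant. A urine pregnancy test will be conducted during the study screening visit". Key inclusion criteria: "Women must be pre-menopausal with regular menstrual cycles", with an age range of 21 to 50. The number of women to be enrolled is not given.

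The Procedures section puts 10 days of logs and actigraphy after the screening visit. It continues: "If they meet the inclusion criteria after this 10d screening period, they will be scheduled to undergo a history and physical at the CTRC", and the baseline assessment and randomisation follow. On timing it says: "Assessments will be conducted at four points: 1) baseline; 2) after completion of condition 1; 3) after the 2 wk wash-out period", the fourth point being the end of condition 2. Under Secondary outcome variable(s): "Metabolic testing and DEXA will occur once at each of the four assessment periods". The procedures describe one common protocol for all four assessments: timed blood draws, fasting bloods, indirect calorimetry and DEXA. They also say that the assessments serve research only and are not part of standard care.

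Potential Study Risks acknowledges the exposure: "This research study involves exposure to radiation from the DEXA scans and therefore participants will receive a radiation dose". It gives 0.04 mrem per scan and does not mention pregnancy.

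The primary outcome is body mass after two months. The Analysis Plan applies intent-to-treat principles, uses all available data in a mixed model, and expects 16 completers. It does not mention pregnancy.

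**The concern.** The protocol makes pregnancy an exclusion and uses a test to enforce it, but the test is done only once, before every scan and every post-randomisation measurement. Women in the trial must be pre-menopausal, and participation lasts about five months, so a pregnancy can begin after the test.

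Two things are at stake. The first is participant protection. The scans have no clinical purpose for these volunteers, so the sponsor should be able to show that its own exclusion is still met when each scan is done. The second is validity. Pregnancy changes body mass, which is the primary outcome, and can affect body composition and the metabolic secondary outcomes. With all available data retained and no stated rule, pregnancy-related weight would enter the condition contrast, and any decision on how to treat it would be made after the fact.

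**Working it through.** **Step 1. Reproduce the plan's duration.** Study duration lists 2 weeks, 2 months, 2 weeks and 2 months. With a month of 365.25/12 = 30.4375 days, 2 months is 60.875 days.

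Total: 14 + 60.875 + 14 + 60.875 = 149.75 days; 149.75/30.4375 = 4.92 months. This agrees with the stated figure of about 5 months.

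Baseline to assessment 4: 60.875 + 14 + 60.875 = 135.75 days = 4.46 months.

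**Step 2. Time from the test to each scan.** Let s be the days from the screening visit to baseline: 10 if only the log period intervenes, 14 if the full two weeks for screening and baseline are used.

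| Scan | Formula | s = 10 | s = 14 |
|---|---|---|---|
| 1, baseline | s | 10 | 14 |
| 2, after condition 1 | s + 60.875 | 71 | 75 |
| 3, after wash-out | s + 74.875 | 85 | 89 |
| 4, after condition 2 | s + 135.75 | 146 | 150 |

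All four scans come after the only stated test, three of them by more than two months.

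**Step 3. Look for a later check.** The assessment procedures name no urine test, no pregnancy or menses query before DEXA, and no action if a participant becomes pregnant. The history and physical at the CTRC before baseline names no pregnancy test. By contrast, eating, sleep and exercise are queried daily, and activity must stay within 30 minutes per week of baseline throughout the study. The visible text has no comparable follow-up of pregnancy status.

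**Step 4. Scale of the effect on the primary contrast (illustration).** Take a balanced two-period cross-over with N completers, N/2 per sequence. Suppose one participant carries extra weight e1 at the end of period 1 and e2 at the end of period 2. The condition estimate is half the difference between the two sequences' mean period differences, so the shift is

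½ × (e2 − e1)/(N/2) = (e2 − e1)/N, with a sign that depends on her sequence.

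Let d = |e2 − e1|. The documents give no value for d; 1 to 4 kg is assumed.

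- N = 16 (Analysis Plan): 1/16 = 0.06 kg to 4/16 = 0.25 kg.
- N = 24 (80% of 30, if all 30 are randomised): 1/24 = 0.04 kg to 4/24 = 0.17 kg.

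For scale only, the two-week cross-over study of 27 males cited in the Background found −0.04 kg versus +0.06 kg, a difference of 0.10 kg. This is the unadjusted contrast; the planned model with baseline and other covariates would give a somewhat different shift.

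**The case against.** The strongest reply is that pregnancy is an eligibility criterion and is tested when eligibility is decided. The test precedes scan 1 by only 10 to 14 days, with a history and physical in between. Afterwards there are daily queries, food deliveries every three days and real-time adverse-event monitoring. The stated dose is small, 4 × 0.04 = 0.16 mrem over the study (the documents' own figure, not verified here), and the study is rated minimal risk. Order is randomised, so a pregnancy adds noise rather than systematically favouring one schedule. The timeline and consent forms are unseen attachments and the listed criteria are headed as key ones, so a repeat test or contraception requirement may exist elsewhere.

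Much of this stands and limits the point. None of the contacts is described as a check for pregnancy, however, and none settles how the data would be used.

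A reader might infer more than the documents support:

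- That the exclusion fails, or that pregnant women are scanned. The absence of a re-test shows only that status is unverified.
- That the declaration under Vulnerable Populations, "None of the above populations are included in the research study", is contradicted. It answers a form item about who is to be enrolled, not about status at each scan.
- That the chance of a case can be stated. With 5 women at 1% per year, or 20 women at 10%, 1 − (1 − r)^(145.75/365.25) gives 0.0040 or 0.0412 per woman. The chance of at least one pregnancy is then about 2% or 57%. Neither the number of women nor the rate is in the documents, and this counts any conception rather than an undetected one at a scan. The range is too wide to rely on.
- That the distortion falls on whichever condition came second. A pregnancy present before baseline or arising in period 1 affects both periods; only the difference e2 − e1 matters.
- That body mass is listed at four assessments. The procedures name a weight measurement only at screening; later ones are implied by the outcome and the design.

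**Conclusion.** The point holds as a gap in verification and in data handling. As written, the visible plan leaves pregnancy status unverified at all four scans, by 10 to 14 days at baseline and 71 to 150 days at assessments 2 to 4, and has no rule for a pregnancy arising during the study or for its data. The intervals rest only on the plan's stated durations.

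The possible shift in the primary contrast, 0.04 to 0.25 kg for one case, rests on the assumed 1 to 4 kg and is illustrative. The conclusion does not depend on it, on any pregnancy rate, or on a claim of large radiation harm. It is subject to the unseen attachments: if they already specify repeat testing, what remains is to state it in the protocol text and add the data-handling rule. The change is worth making because it is small and uses a test already in the protocol, but the gap does not undermine the design.

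**What to change.** 1. Reconcile Key exclusion criteria with Procedures so that pregnancy status is re-verified, using the urine test already in the protocol, at each of the four CTRC admissions before the DEXA.
2. The sponsor should state in the protocol what follows from a positive result for the participant and for the remaining assessments. No clinical rule is proposed here.
3. In the Analysis Plan, keep the intent-to-treat analysis on all available data as primary. Pre-specify a sensitivity analysis of body mass, body composition and metabolic outcomes that omits a participant's assessments from a detected pregnancy onward. The planned mixed model can still use her earlier assessments.
4. Check the study timeline and consent forms against the revised text.

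The cost is up to four inexpensive urine tests per woman at admissions already scheduled, a few sentences in the protocol and, if needed, the consent form, and one extra sensitivity analysis. The procedures list only blood sampling at these admissions, so urine collection would be a small added step. No extra visit is needed.

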
tests, each subject lays supine in bed with his/her head under a plastic canopy which collects the expired air and is told to remain silent and still and to breathe normally. Resting metabolic rate will be measured after a 10 h overnight fast. These metabolic measurements using indirect calorimetry are routinely conducted (and have IRB approval) for our experimental sleep studies (under Co-I [name] leadership). Body composition will then be measured using DEXA at the Presbyterian Hospital CTRC and will be reviewed by study personnel (i.e., our study's medical director, Co-I [name], or Drs. [name] or [name]). The scans will take approximately 30 minutes, during which time the participants lie flat and still. Participants will receive their food and released at the completion of this assessment. None of these assessment would be considered part of standard care as these are healthy participants. All assessments are performed exclusively for research purposes. [name] will serve as the medical director of the study and [name] will be available for urgent issues during assessments. Research staff will deliver meals and snacks from the CTRC metabolic kitchen every 3d, pick up uneaten food, and collect and provide new actigraphs (1/wk). Personalized menus will accompany the meals and participants will check off each food item they consume and note any modifications to their meals and snacks. The CTRC staff will provide portion size training at baseline, and all participants will receive measuring cups. Participants will purchase their own beverages and record them on the menus. Mean beverage intake, as reported at baseline, will be factored into each participant's total daily caloric and macronutrient totals. CTRC staff will provide a diet consisting of approximately 55% carbohydrate, 15% protein, and 30% fat with an isocaloric energy level. These parameters will remain constant across conditions. Staff will send daily queries by text or e-mail to monitor adherence to the eating, sleep, and exercise parameters (Appendix B) and intervene the same day if participants report consuming less than 80% (4/5) of the provided meals and snacks, eating or sleeping outside of the assigned time windows, or exercising more than prescribed. Staff will also download actigraphy data and collect the logs weekly, to monitor compliance. If participants are unable to consume a meal or snack as provided, they will send a picture of their meal or snack using an electronic device, including a reference object, i.e., a card of known dimensions provided by the investigators to orient the staff to the portion size. This template-based approach has been used to develop more sophisticated mobile applications for food intake assessment. All uneaten food will be saved and returned to the metabolic kitchen when staff delivers new food. If it is not possible to save leftover food, participants will take a picture of the remaining food including the reference object. Kitchen staff will pre-weigh all provided items and post-weigh any non-eaten items and compute macronutrient and caloric counts for participants daily intake using the Nutrition Data System for Research (NDSR). [Note: participants will be provided a master meal and snack menu from which they can pick foods that they find acceptable. If participants do not like certain foods, they can alter their selections. Regular contact with participants due to the scheduled food deliveries and daily queries will facilitate these requests. We plan to offset the high study burden by enrolling participants in close proximity to the CTRC, providing them with all meals and snacks for a total of 4 mo at an estimated value of \$1000, and compensating them \$300 for each of 4 CTRC assessments, with a \$300 bonus at study completion (\$1500 total, paid by check). After the first condition (2 mo), participants will complete assessment 2. They will eat according to their usual (baseline) dietary pattern for two weeks, which serves as a wash-out period from the first assigned eating condition. Participants will then complete assessment 3, immediately followed by completion of the second eating condition, followed by assessment 4. All assessments follow the same protocol. Following completion of the fourth assessment, participants will complete a brief survey regarding their perceived adherence to study protocol and explain what they would have changed to make the study easier to adhere to. Appendix A shows the study timeline. Appendix B shows the text/email questions we will use to assess adherence each day. Appendix C shows a sample menu that will be used for participants to identify their food preferences.

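### Does the missing detail on when participants are weighed, and how long they fast before the blood panel, undermine the comparison of eating schedules?

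*Combined protocol and SAP*

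**What the plan says.** The Primary outcome section asks whether meal timing "affects body mass (kg) after a period of two months". It names no visit, clock time or weighing condition. In Procedures, weighing of participants appears once, at the screening visit: "their weight, height, and waist circumference will be measured".

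The four-point schedule is written for the other outcomes: "Our secondary outcomes will be assessed before and after each eating condition for a total of four assessment periods". The Secondary outcome section then names blood samples, metabolic testing and DEXA.

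Procedures describes four inpatient assessments of 28 h. Participants eat on their typical schedule at points 1 and 3, "or their assigned schedule - daytime or delayed (for points 2 and 4"). Blood is drawn every 4 h at fixed clock times, with 0800h listed first. On the panel, the text reads: "Fasting levels of glucose, insulin, adiponectin, cholesterol, triglycerides, and non-esterified fatty acids (NEFAs) will be measured at the beginning of each assessment session".

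A fasting length is given only for indirect calorimetry, on the morning after the draws: "Resting metabolic rate will be measured after a 10 h overnight fast". Potential Study Risks describes the same procedure as "restraining participants from eating for a period of at least 10 hours (overnight"). DEXA comes after calorimetry. Procedures also states: "All assessments follow the same protocol".

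The Analysis Plan regresses every outcome on eating condition and its baseline value, adjusts for period, and allows eating timing among possible adherence covariates. Appendix A (timeline), Appendix B (daily questions) and the grant's science section are listed as attachments but were not available for this review.

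**The concern.** In most trials a missing weighing instruction is trivial. Here the treatment is the time of day at which people eat. If weight or blood is taken at a fixed clock time while the last meal comes later under one schedule, hours since intake differ systematically between conditions. Part of an observed difference would then reflect how recently participants ate, not what two months of the schedule did to them. For weight, food and fluid still in the body would favour the hypothesised direction if last intake is later under delayed eating.

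The design does not remove such a difference. Randomised order does not, because the difference travels with the condition. Baseline adjustment does not, because points 1 and 3 use the typical schedule. An eating-timing covariate cannot separate something that is part of the condition. The weight differences in this field can be small: the Background cites a 2-week crossover with changes of -0.04 and +0.06 kg.

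**Working it through.** The plan states no figure to reproduce, so the check is of the text, with arithmetic for scale only.

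**1. Is a weighing occasion written after screening?** No. The inpatient content is timed draws, the panel, calorimetry and DEXA. The pre- and post-weighing in Procedures is of food items. The history and physical before baseline mentions no weight, and DEXA is named for body composition only.

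**2. Can the occasion be inferred?** Yes, from four places read together. The outcome is body mass at two months. Assessments fall at baseline, after condition 1, after wash-out and after condition 2. Each outcome is modelled with its own baseline. All assessments are run alike. Together these imply a weight at each of the four points. Only the moment within the stay and the conditions remain open.

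**3. Which moments are available?** If the stay starts at the first listed draw, 0800h + 28 h = 1200h the next day. That fits the remaining order: last draw at 0400h, then calorimetry (45 minutes) and DEXA (about 30 minutes). A weight taken on that final morning falls under the stated 10 h fast, apart from fluids. A weight taken at arrival does not.

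**4. How far could the panel fast differ?** The eating windows are not in the supplied text, so last-intake times are assumptions; 2200h to 2400h is bounded by the bedtime limits in Key exclusion criteria.

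| Condition | Assumed last intake | Hours to 0800h draw |
|---|---|---|
| Daytime | 1800h to 2000h | 14 to 12 |
| Delayed | 2200h to 2400h | 10 to 8 |

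Smallest gap: 12 - 10 = 2 h. Largest gap: 14 - 8 = 6 h. A 10 h fast before an 0800h draw would need last intake by 2200h.

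**5. What would this mean for weight?** The cited contrast is 0.06 - (-0.04) = 0.10 kg. To create an artefact of that size, weight would have to drift by 0.10/6 = 0.017 to 0.10/2 = 0.05 kg per hour since intake. The documents give no drift rate.

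**6. What would this mean for the test?** Take the Analysis Plan's 16 completers, 14 degrees of freedom and an assumed SD of paired differences of 1 to 2 kg. Then SE = SD/√16 = 0.25 to 0.50 kg. With no true effect, the rejection rate of a two-sided 5% test comes from a noncentral t distribution with noncentrality bias/SE. An assumed bias of 0.10 kg with SD 2 kg (noncentrality 0.2) gives 5.4%. An assumed bias of 0.50 kg with SD 1 kg (noncentrality 2) gives 46.1%. A range from near nominal to nearly one half shows that the assumptions decide the answer, so it is not evidence about this trial.

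**7. Do the two statements of the calorimetry fast conflict?** No. Procedures gives 10 h, and the risk section describes the discomfort of at least 10 h. They agree if 10 h is a minimum, and a 10 h fast applied at every assessment leaves little ground for concern about respiratory quotient.

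**The case for a change.** The strongest case for a change is that a primary outcome should have a written measurement procedure, above all when the intervention could contaminate it. Procedures gives posture and adaptation minutes for calorimetry but says nothing about food, drink, voiding, clothing or scale at weighing. An occasion can be inferred; those conditions cannot. Running every assessment alike does not help, since the same clock time with different meal times is how unequal fasts would arise. The 10 h fast cannot be carried back to the panel, because the panel opens the session and the fast precedes the following morning's calorimetry. A few sentences would close the gap.

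Much of this stands: the omissions are real, and the crossover would not cancel a difference that comes with the condition. What does not stand is the step from missing detail to a defective plan. The harm needs three things to hold together: weight taken outside the overnight fast, last intake differing by condition beforehand, and a material residual mass. None can be shown from the documents. The panel is labelled fasting; only the duration is unwritten. The information is not lost either: food logs run throughout, menus and daily queries track meals, and food during the stay is eaten at the research center. Hours since last intake may therefore be recoverable, although nothing requires that they be tabulated.

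The one substantive choice, whether to hold hours since intake or clock time equal, is a genuine trade-off. Later eating is what the delayed condition consists of, and either choice can be defended.

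**Conclusion.** No change is called for. The supplied text does not say when in each stay, or under what conditions, body mass is measured, and it gives no fasting length for the panel. This is missing operating detail, which competent staff fill sensibly: with fasted morning weighing done the same way at all four assessments, the plan is sound as it stands. The attachments that were not available may already contain the detail.

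The size of any bias is unknown. The 2 to 6 h gap rests on assumed meal times and an assumed 0800h panel. The false-positive rates rest on assumed biases and SDs and should carry no weight. The respiratory-quotient worry and the supposed conflict between the two fasting statements fall away. The conclusion would change if the trial's own eating windows or visit records showed weight taken after clearly unequal intervals since eating. Nothing in the documents shows that.
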